Specifically, this study aims to compare the efficacy of hydrocolloid dressing after 5 days post-punch biopsy by measuring the following parameters: absence or presence of infection, clinical estimate of reepithelialization, clinical estimate of wound closure, scar formation, pigmentation of scar and cosmetic appearance of wound.

METHODOLOGY

A. Study Design

This is a double blind randomized controlled trial that will be conducted at the outpatient department of the University of Santo Tomas Hospital Department of Dermatology. Permission letters from the Head of Ambulatory Care Services (ACS), the Data Privacy Officer (DPO), and the Medical Director of UST Hospital will be obtained prior to the implementation of this study. Permission letters from the USTH Dermatology consultants for their private patients will be obtained prior to the implementation of this study.

[figure not shown]

Figure 1. Schematic diagram of the study design

B. Patient Selection, Recruitment and Withdrawal

Adult patients 18 to 64 years old with clean cutaneous lesions who will undergo skin punch biopsy using a 3-mm disposable biopsy puncher shall be included in the study.

Patients will be recruited from the UST Hospital outpatient department and from the private clinics of the UST Hospital Dermatology consultants. Patients who have infected wounds, patients who have conditions with poor tendency to heal including diabetes mellitus, peripheral vascular disease, history of keloid formation, patients currently receiving anticoagulation therapy or systemic corticosteroids, and patients known to have hypersensitivity to topical antibiotics shall be excluded from the study.

Participants may request to withdraw from the study at any time. A participant may also be withdrawn from the study if the primary investigator believes that the participant was non-compliant with the treatment guidelines or develops severe and intolerable adverse effects (e.g. hypersensitivity reaction) secondary to the treatment given.

C. Randomization and Blinding

Randomization

Assignment of participants to the experimental (hydrocolloid dressing) or control group (topical antibiotic) will be done using the fishbowl method by a research assistant.

Blinding

Participants and the physician assessors will be blinded with the treatment assigned.

D. Baseline Data Collection

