On the first visit, informed consent will be obtained from the patient. Afterwards, the following data will be recorded by the primary investigator on the baseline general information sheet: study code assigned to each individual patient, age, sex, and anatomic sites involved.

Photographs will be limited to the skin punch biopsy sites and will be taken at baseline using a DSLR camera with uniform distance (3 inches) and lighting.

On the 5th day after the skin punch biopsy procedure, the following data will be recorded by the physician assessors: the presence or absence of infection, the clinical estimate of reepithelialization, the clinical estimate of wound closure, scar formation, pigmentation of scar, and the cosmetic appearance of the wound. The primary investigator will then collect the wound evaluation sheets from the physician assessors. Photographs of the biopsy site will also be taken.

E. Intervention

Before the biopsies will be performed, the sites will be cleansed with 70% isopropyl alcohol and anesthetized intradermally with 1% lidocaine hydrochloride.

No suture, electrocautery, aluminum chloride or other hemostatic agents will be applied to the biopsy sites to avoid inhibition of wound healing inherent with these agents.

Once bleeding will be controlled by pressure, wounds will be dressed with either a 1-inch size Duoderm Control Gel Formula hydrocolloid dressing or gauze dressing impregnated with mupirocin ointment covered by a transparent dressing (Tegaderm). Dressings will be left in place for 5 days, after which the dressings will be removed and will be cleansed with water to remove any exudate.

F. Assessment

For this study, wound assessment will be done after 5 days. Dermoscopy and photographs of the wounds will be taken for every evaluation.

According to a study entitled “Pathophysiology of Acute Wound Healing” by [name] et. al. published in Elsevier Clinics in Dermatology in 2007, there are three phases of wound repair that overlap in time. These are the inflammatory reaction phase, proliferation phase, and remodeling phase. Days after initial injury, the wound would be in the proliferative phase where there would be reepithelialization of the wound, the establishment of appropriate blood supply, and reinforcement of the injured dermal tissue.^[14]

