Three physician assessors who will be trained in the evaluation of skin punch biopsy wounds and the scoring criteria that will be used in this study will assess the wound and record their evaluations individually.

SAMPLE SIZE AND STATISTICAL ANALYSIS

Using G*Power 3.1.9.7, a minimum of 56 patients or 28 per group are required for this study based on the 8.38 mean Scar appearance score on Hydrocolloid

dressing versus 7.23 mean Scar appearance score on Conventional daily dressing.^[15] This computation also accounts for desired 1.5 common standard deviation, 5% level of significance and 80% power.

Descriptive statistics will be used to summarize the demographic and clinical characteristics of the patients. Frequency and proportion will be used for categorical variables and mean and SD for normally distributed continuous variables. Independent Sample T-test and Fisher's Exact/Chi-square test will be used to determine the difference of mean and frequency, respectively, between patients undergoing Hydrocolloid Dressing versus Topical Antibiotic. All statistical tests will be two tailed tests. Shapiro-Wilk test will be used to test the normality of the continuous variables. Missing values will neither be replaced nor estimated. Null hypotheses will be rejected at 0.05 α -level of significance. STATA 13.1 will be used for data analysis.

Inter-rater and Intra-rater reliability will also be conducted.

SAFETY EVALUATION

Assessment of possible adverse effects due to the hydrocolloid dressing or the topical antibiotics will be done on follow-up visit. Complaints of pruritus, burning, or stinging sensation will be asked from participants, while other physical signs and symptoms of adverse effects to the treatment applied will be checked by the primary investigator.

ETHICAL CONSIDERATIONS

This study will be conducted in accordance with the accepted ethical research practices of the ICH Good Clinical Practice regulations and guidelines. The study will

be explained thoroughly to the eligible patients prior to enrollment. Free and informed written consent will be obtained.

INFORMED CONSENT

All participants involved in the study will not be compromised in terms of treatment. All possible benefits and side effects of the treatment will be fully explained and must be understood by the patients prior to enrollment into the study.

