The possible side effect of hydrocolloid dressing is irritation of the skin. Treatment on patients who will experience any adverse side effects will be immediately stopped.

To minimize the risk of COVID-19 exposure, all safety measures in accordance with the IATF guidelines will be observed.

BENEFITS

The benefit that the patient will acquire from this study is better clinical outcomes of the post-biopsy site. This study can also help reduce medical costs and patients are suggested with alternative options which can be potentially used as one of the treatment modalities for post-biopsy sites.

INCENTIVES AND COMPENSATION

All of the dermatologic consultations and medications of the participants for the duration of the study will be free of charge. Transportation allowance of PHP 100.00 will be provided to the participant on their visit on the 5th day. Management, consultation, and treatment of adverse effects resulting from the participation in this study will be free of charge. No other form of monetary compensation will be provided to the patients for their participation. Patients will be informed of the results of the study once it has been completed.

SCORING CRITERIA FOR EVALUATION OF WOUND

Objective assessment is based on a study by Armstrong et. al. in 1986 entitled "Punch biopsy wounds treated with Monsel's solution or a collagen matrix".^[16] For this study, the assessment will be done as follows:

(1) infection (absent, millimeters of surrounding erythema or equivocal findings; or present, as inferred by indurated erythema or purulent discharge);

- (2) clinical estimate of reepithelialization (rated on a scale of (a) 0% to 25%, (b) 26% to 50%, (c) 51% to 75%, and (d) 76% to 100%);
- (3) clinical estimate of wound closure (rated on a scale of (a) 0% to 25%, (b) 26% to 50%, (c) 51% to 75%, and (d) 76% to 100%)
- (4) scar formation (unhealed; depressed or atrophied; normal fine-line scar; or hypertrophied scar or keloid);
- (5) pigmentation of scar (indeterminate or unhealed; normal; hyperpigmented; or hypopigmented);
- (6) cosmetic appearance of wound (acceptance of patient: indeterminate or unhealed; poor; fair; good; excellent)

DUMMY TABLES

Table 1. Baseline demographic and clinical characteristics

	Total	Hydrocolloid	Topical	P-value
		Dressing	Antibiotic	
Frequency (%); Mean \pm SD				
Age, years				
Sex				
Male				
Female				
Indications for Skin				
Punch Biopsy				
...				

Table 2. Scoring Criteria for Evaluation of Wound

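### Physical signs of adverse effects are checked by the primary investigator, who is not listed as blinded, although three blinded assessors examine the same site on day 5

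*Combined protocol and SAP*

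**What the plan says.** The Blinding paragraph (Methodology, section C) names two blinded groups: "Participants and the physician assessors will be blinded with the treatment assigned". The primary investigator is not one of them.

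Safety Evaluation sets the time of the check: "Assessment of possible adverse effects due to the hydrocolloid dressing or the topical antibiotics will be done on follow-up visit". Participants are asked about pruritus, burning and stinging, while "other physical signs and symptoms of adverse effects to the treatment applied will be checked by the primary investigator".

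The Assessment section gives the time of wound scoring: "For this study, wound assessment will be done after 5 days". It is done by "Three physician assessors who will be trained in the evaluation of skin punch biopsy wounds", who record their evaluations individually. The investigator's role is separate from theirs. Baseline Data Collection (section D) says: "The primary investigator will then collect the wound evaluation sheets from the physician assessors".

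The assessors score six items. The infection item already directs them to the skin around the wound: "infection (absent, millimeters of surrounding erythema or equivocal findings; or present, as inferred by indurated erythema or purulent discharge". None of the six items records a skin reaction or other adverse effect.

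The Risks section names one side effect, for one arm: "The possible side effect of hydrocolloid dressing is irritation of the skin". Dummy Tables 1 and 2 have no adverse-effect rows.

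**The concern.** Mild skin reactions are a matter of judgement, and the protocol gives no definition or scale for them. A rater who knows the dressing can be swayed in either direction. The Risks section, which ties irritation to the hydrocolloid, could lead such a rater to call it more readily in that arm. The Benefits section, which expects better clinical outcomes, could lead the same rater to play it down. Blinding the rater guards against both.

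The protocol has arranged that protection for the wound scores but has not stated it for the signs of harm. Irritation is the only side effect that the Risks section names for the experimental dressing. If the trial later reports skin reactions by arm, readers will ask who judged them and whether that person was blinded, and the protocol as written has no good answer. Meanwhile, three trained and blinded raters will have looked at the same skin on the same day without being asked to record what they saw as a skin reaction.

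**Working it through.** **The plan's own figure.** The only calculation in the document is the sample size. Inputs, from Sample Size and Statistical Analysis: means 8.38 and 7.23, common SD 1.5, two-sided 5% level, 80% power.

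- Standardised difference: (8.38 − 7.23) / 1.5 = 1.15 / 1.5 = 0.767.
- The noncentral t calculation for two independent groups gives 27.70 per group, rounded up to 28, or 56 in total. Power at 28 per group is 80.4%.

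The stated figure is reproduced. It concerns a scar score and does not depend on who checks for adverse effects.

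**Comparison of the sections.**

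1. *Who is blinded?* Participants and physician assessors (section C).
2. *Who checks physical signs of adverse effects?* The primary investigator (Safety Evaluation).
3. *Could the investigator be one of the assessors, and so be covered?* The text points the other way, because the investigator collects the assessors' sheets (section D).
4. *Is allocation kept from the investigator elsewhere?* No section says so. A research assistant makes the assignment. Who applies and who removes the dressings is not stated.
5. *Are blinded raters present at the same time?* Yes. The safety check is at the follow-up visit, and day 5 is the only one described. The transport allowance under Incentives and Compensation also refers only to the fifth-day visit.
6. *Do the blinded raters look at the relevant skin?* Yes, at least for redness. Under the infection item, however, millimetres of surrounding erythema fall in the *absent* category, so the observation is not kept as a skin reaction.
7. *Is a between-arm comparison of adverse effects planned?* Not explicitly. The tests named are generic, and neither dummy table has such a row.

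**Illustration of size.** The documents give no adverse-effect rates, so the following rates are assumptions. Suppose that true mild irritation is 15% in both arms: 28 × 0.15 = 4.2, or about 4 of 28 in each. The table shows what happens if doubtful cases are called in one arm only.

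| Extra calls in one arm | Counts | Percentages | Fisher's exact p (two-sided) |
|---|---|---|---|
| 0 | 4 v 4 | 14.3% v 14.3% | 1.00 |
| 3 | 7 v 4 | 25.0% v 14.3% | 0.50 |
| 7 | 11 v 4 | 39.3% v 14.3% | 0.07 |
| 8 | 12 v 4 | 42.9% v 14.3% | 0.04 |

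On this assumption, a few one-sided calls would shift the descriptive percentages visibly, but it would take eight to produce a significant difference.

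**The case against.** The strongest reply is that the section describes ordinary safety oversight by a responsible physician and not a measured outcome. Irritation is not among the six parameters, has no table and has no named test, so there is no planned comparison to bias. This stands as far as it goes. The point therefore concerns any by-arm report of skin signs that the trial may make, and not a defective analysis already in the plan.

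A reader might infer that the investigator is unblinded. The documents do not support that. They leave this role out of the blinded list and describe no concealment from it, but they do not say that the investigator knows the allocation. Recording study codes at baseline and having access to the collected data do not show it either.

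A reader might also infer that suspicion of harm is directed at one arm only. The Risks section reads that way, but Safety Evaluation checks for effects of both treatments. The eligibility and withdrawal criteria also anticipate hypersensitivity, including to topical antibiotics. The direction of any bias is therefore not settled.

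Nor should the infection item be read as a second, conflicting measurement of irritation. It classifies infection, which is a different construct from tolerability. Its relevance is only that the blinded assessors already look at the surrounding skin.

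Finally, the example of 7 against 4 rests on assumed rates and is far from significant. It shows how few calls move a percentage at this sample size and does not estimate the bias. What remains is that a better-protected reading is available at the same visit for very little effort.

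**Conclusion.** The point holds as a cheap improvement of minor severity. Physical signs of adverse effects are assigned to a rater whose blinding is not stated, while three raters whose blinding is stated examine the same site at the only follow-up visit. Any between-arm statement about local skin signs would lack the protection that the trial gives its wound scores.

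The size of the bias cannot be derived from the documents. The conclusion rests on two readings of the text: that the investigator is not one of the three assessors, and that the follow-up visit in Safety Evaluation is the day 5 visit. It is confined to signs. Pruritus, burning and stinging are reported by participants, who are listed as blinded. The efficacy scores and the sample size do not change.

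**What to change.** - Add local skin signs to the wound evaluation sheet that the three blinded assessors already complete on day 5, for example peri-wound erythema in millimetres, and vesiculation, maceration or dermatitis as yes/no.
- Say in the analysis section that any between-arm summary of skin signs will use the assessors' reading.
- Add the corresponding rows, by arm, to the dummy tables; Table 2 is the natural place.
- Leave the symptom questions and the investigator's safety oversight and event management as written.

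The cost is a few lines on an existing form and a few table rows, with slightly longer scoring per wound. No extra staff, visit or participants are needed. The inter-rater reliability analysis already planned could cover the new items as well.

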	Total	Hydrocolloid	Topical	P-value
		Dressing	Antibiotic	
Frequency (%)				
Infection				
Absent				
Present				
Re-epithelialization estimate				
0 to 25%				
26 to 50%				
51 to 75%				
76 to 100%				
Wound closure				
0 to 25%				
26 to 50%				
51 to 75%				
76 to 100%				
Scar Formation				
Unhealed				

Depressed or Atrophied

Normal Fine-Line Scar

Hypertrophied Scar or
Keloid

Scar Pigmentation

Indeterminate or Unhealed

Normal

Hyperpigmented

Hypopigmented

Cosmetic Appearance

Indeterminate or Unhealed

Poor

Fair

Good

Excellent

REFERENCES

2. Mendonça RJ de, Coutinho-Netto J. Cellular aspects of wound healing. *Anais Brasileiros de Dermatologia*. 2009;84(3):257-262.
doi:<https://doi.org/10.1590/s0365-05962009000300007>
3. Lazarus GS. Definitions and Guidelines for Assessment of Wounds and Evaluation of Healing. *Archives of Dermatology*. 1994;130(4):489.
doi:<https://doi.org/10.1001/archderm.1994.01690040093015>
doi:<https://doi.org/10.1097/01.asw.0000416006.55218.d0>
5. Thomas S. Hydrocolloid dressings in the management of acute wounds: a review of the literature. *International Wound Journal*. 2008;5(5):602-613.
doi:<https://doi.org/10.1111/j.1742-481x.2008.00541.x>
6. Viciano, José E. Castera, J V. Effect of Hydrocolloid Dressings on Healing by Second Intention after Excision of Pilonidal Sinus. *The European Journal of Surgery*. 2000;166(3):229-232.
doi:<https://doi.org/10.1080/110241500750009339>

doi:<https://doi.org/10.1097/00000637-199401000-00011>
9. Hultén L. Dressings for surgical wounds. *The American Journal of Surgery*. 1994;167(1A):S42-S45. doi:[https://doi.org/10.1016/0002-9610\(94\)90010-8](https://doi.org/10.1016/0002-9610(94)90010-8)

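### Re-epithelialization and wound closure are ordered percentage estimates, but they are kept only in four bands and compared with a test that ignores band order, which costs power

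*Combined protocol and SAP*

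**What the plan says.** **Recording.** In Scoring Criteria for Evaluation of Wound, item 3 is "clinical estimate of wound closure (rated on a scale of (a) 0% to 25%, (b) 26% to 50%, (c) 51% to 75", with a fourth band of 76% to 100%. Item 2, re-epithelialization, uses the same four bands. The other four items (infection, scar formation, pigmentation, cosmetic appearance) are categories.

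**Reporting.** Dummy Table 2 lists "Re-epithelialization estimate" and wound closure by band, as counts with percentages and a P-value. It has no row for a mean and SD.

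**Analysis.** Sample Size and Statistical Analysis assigns the independent t-test to means and Fisher's exact or chi-square to frequencies. It adds that "Shapiro-Wilk test will be used to test the normality of the continuous variables" and that "All statistical tests will be two tailed tests". No test for ordered categories is named.

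**Sizing.** The same section says "a minimum of 56 patients or 28 per group are required for this study". The inputs are average scar scores of 8.38 (hydrocolloid) and 7.23 (comparison dressing), together with "desired 1.5 common standard deviation, 5% level of significance and 80% power".

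**Assessors.** There is one outcome assessment, at day 5. Three trained assessors score each wound separately. The plan does not say how their ratings are combined.

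**The concern.** Both items measure a quantity that runs from 0 to 100%, so their categories have a natural order. The plan gives up information in two steps.

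1. The form keeps only the band, so a wound at 76% and a wound at 100% become the same observation.
2. The test implied by Table 2 treats the four bands as unordered labels.

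If hydrocolloid shifts wounds upwards by a moderate amount, a test that uses the order has a better chance of showing it than one that does not. With 28 per arm and one assessment, a real difference on either item could be missed, and detail not written down on day 5 cannot be recovered from a later visit.

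**Working it through.** **1. The plan's own figure.** Difference 8.38 − 7.23 = 1.15; SD 1.5; d = 1.15 / 1.5 = 0.767. The normal approximation gives n = 2(1.960 + 0.842)² / 0.767² ≈ 26.7, so 27 per group. The noncentral-t solution is 27.70, so 28 per group and 56 in all, with power 80.4%. The stated size reproduces for a two-sided t-test on a mean scar appearance score.

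**2. Why the planned test ignores order.** Pearson's statistic is the sum of (O − E)² / E over the 2 × 4 table, on 3 df. Rearranging the four columns leaves it unchanged. Fisher's exact test has the same property.

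**3. What banding alone costs a rank test.** The approximate efficiency of bands against the ungrouped value is 1 − Σp³, where p is the share of wounds in each band.
- Even bands: 1 − 4 × 0.25³ = 0.94.
- 60% in the top band: at most 1 − 0.60³ = 0.78; about 0.77 after the other bands are subtracted.
- 70% in the top band: at most 1 − 0.70³ = 0.66; about 0.65 after the other bands.

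**4. Illustrative power.** All of these inputs are assumptions: percentage = inverse logit of Normal(μ, 1.2), rounded to 5%; a shift of 0.767 SD between arms; 28 per arm; two-sided 0.05. After rounding, the top band means a value of at least 77.5%, and logit(0.775) = 1.237. With μ = 0, 1.0 and 1.8, the control share in that band is P(Z > (1.237 − μ) / 1.2) = 15%, 42% and 68%. Two independent runs (4,000 and 2,000 trials per setting, Monte Carlo standard error about 1 point) gave:

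| Controls in top band | Rank test, percentage | Rank test, bands | Chi-square, bands | Lost to banding | Lost to order-blind test |
|---|---|---|---|---|---|
| 15% | 77, 79 | 74, 75 | 56, 58 | 3, 4 | 18, 17 |
| 42% | 78, 79 | 66, 64 | 47, 47 | 12, 15 | 19, 17 |
| 68% | 76, 76 | 50, 52 | 33, 34 | 26, 24 | 17, 18 |

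The last two columns are differences between neighbouring columns, in points. The order-blind test costs about 17-19 points throughout. Banding costs 3-4 points when wounds spread out and 24-26 when they cluster at the top.

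**5. Another distribution.** With a normal percentage clipped to 0-100 and the same d, a t-test on the percentage has 77-81% power. Chi-square on bands has 53-58% at control means of 40-60% (SD 20-30) and 35-45% at control means of 80-85% (SD 10-15). In the extreme case (mean 85%, SD 10) the rank test on bands also falls to 35%, so there an ordinal test recovers nothing.

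**6. Rater error.** Adding single-rater error of SD 10 or 15 percentage points to the model in step 4 lowers power for every method. With SD 10 and 15% of controls in the top band, it is about 72% (percentage), 68% (rank on bands) and 49% (chi-square). With SD 15 and 68%, it is about 36%, 31% and 18%. Across the six noisy settings the cost of banding is about 2-7 points, and the percentage with a rank test stays 16-25 points ahead of chi-square. If three raters are averaged, each with error of 0.5 between-wound SD, the rank test on the mean percentage against the mean band gives 72% v 71%, 75% v 69% and 75% v 59%. The banding cost is then 1, 6 and 16 points.

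**The case against.** The strongest reply is that the form is not the main culprit. When wounds spread over the bands, a rank test on the existing bands comes within 3-4 points of the percentage, so a change of test would do most of the work. That stands. Banding dominates only under clustering in the top band, and nothing in the document shows where wounds will lie on day 5; it says only that re-epithelialization should then be under way.

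A second reply is that visual percentages of a 3-mm wound are imprecise, that a rater may choose a quarter directly without forming a percentage, and that the bands follow a published instrument. The imprecision is real and shrinks the gain, as step 6 shows. The instrument is not lost, because its bands can be derived from the recorded percentage.

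A reader might infer that the t-test and Shapiro-Wilk test have no use at all. The document does not support that: age appears in Dummy Table 1 as mean and SD with a P-value. It is true that no efficacy outcome is continuous, but that follows from all six items being categorical and not from these two alone.

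**Conclusion.** The point holds as a loss of power in the planned comparison of two outcomes. Under the step 4 assumptions, power is about 76-79% for a rank test on the percentage, 50-75% for a rank test on the bands and 33-58% for chi-square. The figures rest on a borrowed effect size and an assumed distribution, so they show direction and rough size only. The order-blind test is the steady part of the loss; the bands add much only if wounds cluster at the top.

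A reader might also infer that recording percentages would bring the trial back to its stated 80% power. The document does not support this. The 80% belongs to a scar appearance score that is not among the six recorded items, nothing shows that d = 0.767 applies to re-epithelialization or closure, and the stated primary outcome is a proportion with better overall healing, which is left undefined. Those gaps need separate repair.

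**What to change.** Before data collection:

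- On the evaluation sheet, have each assessor record re-epithelialization and wound closure to the nearest 5%, from 0 to 100.
- Derive the four bands from these values, so that Table 2 stays as it is, as a descriptive table.
- State in advance how the three assessors' values are combined, for example by the mean or the median.
- Compare the arms on the combined percentage with a two-sided Wilcoxon rank-sum test.
- If only bands are kept, replace chi-square with an ordinal test (Wilcoxon rank-sum or proportional odds).

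The cost is one changed field per item and a few sentences in the analysis section. The downside is that visual percentages are approximate; the derived bands remain as a fallback.
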